1.3 Secondary Study Endpoints

Secondary endpoints include exhaled CO, Kessler-6 score, and cigarette/e-cigarette dependence using Penn State Cigarette Dependence Index (PSCDI) and Penn State Electronic Cigarette Dependence Index (PSECDI), at week 16, and cigarette abstinence (no cigarette use in the past 7 days and CO < 6ppm) at week 20.

Additional endpoints include:

Health effects and toxicant exposure measures: Pulmonary Function Tests (PFT), Clinical COPD Questionnaire (CCQ), urinary CYMA (biomarker for acrylonitrile [volatile organic compound] exposure), 3HPMA (biomarker for acrolein [volatile organic compound] exposure, cotinine (biomarker of nicotine exposure)

Mental health measures: Center for Epidemiological Studies-Depression (CES-D), Overall Anxiety Severity and Impairment Scale (OASIS), Quick Inventory or Depressive Symptomatology (QIDS), Perceived Stress Scale (PSS)

Nicotine/Tobacco use and addiction measures: daily cigarette use, daily e-cig use, Fagerstrom Test for Nicotine Dependence (FTND), Hooked on Nicotine Checklist (HONC), , Minnesota Nicotine Withdrawal Scale (MNWS)

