8.0 Subject Numbers and Statistical Plan

8.1 Number of Subjects

We plan to enroll 300 participants in order to randomize 240 participants (60 in each of the four study arms).

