8.2 Sample size determination

For the sample size calculation, we have used data for completers of our recent randomized controlled trial(8) to estimate magnitude of effects for the primary endpoint (NNAL, pmol/mg creatinine). Additionally, we have used data from Donny et al.'s trial [Table Supplement 15] (5). Based on their paper, the difference in log NNAL between the 0.4 mg/g group (sample size 96) and the 15.8 mg/g group (sample size 100) is $\log(0.78) = -0.248$ with a confidence interval of $\log(c(0.64, 0.96)) = (-0.446, -0.0408)$. Based on this, the within group standard deviation of log NNAL is 0.562. Combining the above two datasets, we shall assume that the effect size is 58% of the size of the standard deviation in the sample size calculation, slightly larger than reported above because our trial will have 16 weeks of follow-up. Let arm 3 of the trial be the group to which arms 1, 2 and 4 will each be compared. To adjust for multiple comparisons, the type one error level alpha is taken to be $.05/3=0.017$. The sample size of 60 subjects in each of the 4 arms is needed to provide 80% power of detecting a difference between any three arms and arm 3. In addition this trial will have over 95% power, at a 5% type 1 error rate, to detect the same effect on abstinence found in our recent RCT of VLNCs one month after the end of the randomized phase (20.2% in those randomized to VLNCs vs. 6.4% in those randomized to NNCs).

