8.3 Statistical methods

Basic baseline statistics including means (standard deviations) and frequency distributions (percentages) will be reported for demographic characteristics, smoking characteristics, nicotine dependence, and nicotine and toxicant exposure. Characteristics will be reported by the four treatment arms to identify treatment arm imbalances. Numerical baseline characteristics will be compared among four arms using ANOVA tests or nonparametric Kruskal-Wallis tests when appropriate. Categorical variables will be compared using chi-square tests or Fisher's exact tests. The focus of the statistical analysis will be the difference between four trial arms in terms of the biomarkers of toxicity and health effects. Analyses will be conducted in two approaches, which will address our research questions in two different angles. The first approach is a simplified and streamlined one, the longitudinal measurements of these biomarkers over the 16-week period will be summarized by using just the baseline (visit 3, pre-randomization) and final (visit 7, end of randomization period) measurements. Analysis of Covariance (ANCOVA) models will be used to compare the final measurements among the four arms, while the baseline measurements will be treated as controlled covariates in the model. Specifically, the comparisons between arms 1 and 3 and between arms 2 and 4 answer whether switching to very low nicotine cigarettes leads to lower markers of harm as compared to continuing on normal nicotine cigarettes. This addresses specific Aim 1. Furthermore, we will study if this reduction is the same when combined with 5% nicotine e-cigs (arms 1 and 3) and combined with placebo e-cigs (arms 2 and 4). Similarly, comparison between arm 1 and arm 2 reveals if access to nicotine versus placebo e-cigs impacts these biomarkers. This will address Aim 2. In particular, we will test if the arm 3 has the best outcome as stipulated in Aim 2. These analyses will be conducted using ANCOVA models with interaction terms between traditional cigarettes (normal nicotine vs. very low nicotine) and e-cig (5% vs. 0%). Appropriate transformation may be done on some of the outcome variables (for example log-transformation) to make sure the underlying statistical assumptions are all satisfied. Note that for NNAL, one of our main biomarkers of toxicity; it can only be analyzed using the first approach due to the limitation of number of measures.

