Intent-to-treat (ITT) principle will be adopted for the analyses in both approaches. Additionally, the measurements of tobacco use and addiction and measurements of mental health will be monitored and summarized, and will be compared across these arms in a similar statistical fashion as described above. Self-reported compliance will be reported for all participants. For participants in arm 4 (VLNC plus placebo ecigs) their compliances will be further evaluated using biomarkers. Comparison on the outcome variables will be made between compliers vs non-compliers within arm 4 participants only. All analyses will be conducted using statistical software SAS version 9.4 or higher (SAS Institute, Cary, NC, USA) and R Programming language version 3.6.1 or higher (R Foundations). All tests will be two-sided and the statistical significance level to be used is 0.05.

Adjusted models will evaluate the treatment effect while adjusting for covariates, such as gender, age, race, SDOH scoring, and other baseline factors.

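### The power stated for week-20 abstinence, over 95%, does not follow from the plan's own inputs; 20.2% vs 6.4% with 120 per group gives about 89% at two-sided 5%.

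*Combined protocol and SAP*

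**What the plan says.** After the NNAL calculation, section 8.2 adds a power statement for abstinence one month after the randomised phase: "In addition this trial will have over 95% power, at a 5% type 1 error rate, to detect the same effect on abstinence" found in the team's recent trial, given there as "20.2% in those randomized to VLNCs vs. 6.4% in those randomized to NNCs". It states no sample size, test, sidedness or loss to follow-up for this figure.

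The other inputs are elsewhere in the same document. Section 8.1 plans to "randomize 240 participants (60 in each of the four study arms"), and section 7.4.3 allocates 1:1:1:1. Aim 3 in section 1.1 compares VLNC with NNC cigarettes. Section 8.3 adopts intention to treat and says: "All tests will be two-sided and the statistical significance level to be used is 0.05". Section 1.3 lists as a secondary endpoint "cigarette abstinence (no cigarette use in the past 7 days and CO < 6ppm) at week 20".

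**The concern.** The two abstinence rates differ by 13.8 percentage points, and 120 per group is a modest number for separating two proportions of this size with 95% power. A rough check already falls short, so the figure had to be recalculated.

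This is the only power statement the plan makes for abstinence, which is both a named secondary endpoint and Aim 3(b). A claim of over 95% tells the reader that the trial would miss an effect of the stated size less than once in twenty times. If the true figure is nearer one in nine, anyone relying on section 8.2 to weigh a non-significant abstinence result would give it more weight than the design supports.

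**Working it through.** **Inputs**

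- VLNC rate p1 = 0.202 and NNC rate p2 = 0.064 (section 8.2), so the difference is d = 0.138.
- Type I error 0.05 (section 8.2). The 0.05/3 split in that section belongs to the NNAL arm comparisons.
- Two-sided test (section 8.3), so z = 1.960.
- n = 120 per group: 60 per arm (section 8.1), arms 3+4 against arms 1+2. Everyone randomised is counted and no loss is assumed, which is the case most favourable to the plan.

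**Attempt to reproduce the stated figure (pooled z-test)**

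Power = Φ[(d − z·SE0) / SE1], where

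- mean rate = (0.202 + 0.064)/2 = 0.133
- SE0 = √(2 × 0.133 × 0.867 / 120) = 0.04384
- SE1 = √((0.202 × 0.798 + 0.064 × 0.936) / 120) = 0.04292

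Power = Φ[(0.138 − 1.960 × 0.04384) / 0.04292] = Φ(1.213) = **88.7%**. The stated value of over 95% is not reproduced.

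**Does the choice of method matter?** At 120 versus 120:

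| Method | Two-sided 5% | One-sided 5% |
|---|---|---|
| Pooled z | 88.7% | 93.8% |
| Unpooled z | 89.5% | 94.2% |
| Likelihood ratio | 89.6% | 94.2% |
| Arcsine | 90.3% | 94.7% |
| Chi-square, exact power | 90.2% | 94.9% |
| Fisher's exact test | 86.2% | 92.0% |
| Log odds ratio (Wald) | 85.0% | 91.2% |
| Continuity-corrected z | 84.6% | 91.0% |

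No two-sided method comes within four points of 95%, and no one-sided method exceeds it.

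**Other inputs that might explain the figure**

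- 150 per group, that is, the 300 enrolled: 94.4% two-sided by pooled z, 95.4% by arcsine, and 97.2% one-sided by pooled z. But the plan says "We plan to enroll 300 participants in order to randomize 240 participants (60 in each of the four study arms"), so the other 60 are never assigned to an arm.
- The earlier trial's 12-week quit rates in section 2.2 (17/94 versus 4/94) at 120 per group: 93.0% two-sided, 96.4% one-sided. These are not the rates that section 8.2 cites.
- 60 versus 60: 60.7%. One arm against the other three (60 versus 180): 82.3%.

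So 95% is passed only by replacing a stated input: 300 for 240 by arcsine, or 300 or the 12-week rates together with a one-sided test.

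**What 95% would take (two-sided 5%)**

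n per group = [1.960 × √(2 × 0.133 × 0.867) + 1.645 × √(0.202 × 0.798 + 0.064 × 0.936)]² / 0.138² = (0.9412 + 0.7734)² / 0.01904 = 154.4, so **155 per group, 310 randomised**. The arcsine formula gives 147, unpooled z 151, Fisher 161 and the continuity correction 169. With n fixed at 120 and NNC at 6.4%, the VLNC rate would have to be about 22.0% to 22.6% by the z and arcsine formulas (23.1% with Fisher), not 20.2%.

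**Sensitivity to loss.** If only completers were analysed and 10%, 15% or 20% were lost (assumed values; the plan gives none for this endpoint), pooled-z power would be 85.3%, 83.2% or 80.9%.

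**The case against.** The best defence is that section 8.2 does not say whether its 5% is one-sided or two-sided, and that the two-sided rule stands under statistical methods, not under sample size. A one-sided calculation gives up to 94.9%, which could have been rounded to 95%. That may well be how the figure arose, but it is still not over 95%, and section 8.3 applies its two-sided rule to all tests.

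A second point is that the plan names no test for abstinence. The sentence in section 8.3, "Categorical variables will be compared using chi-square tests", sits among the baseline comparisons and does not settle it. That is fair, and it is why a range of methods is shown; the conclusion is the same for every one of them.

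Third, the consequence is limited. About 89% exceeds the 80% that the plan accepts for its primary endpoint, and a finished trial is read from its estimate and confidence interval, not from a planning sentence. This stands. It bears on how serious the error is, not on whether the figure is right.

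**Conclusion.** The stated power is wrong on the plan's own inputs. It is about 89% (roughly 85% to 90% by method), not over 95%. The type II error is 11.3% by the pooled formula (100 − 88.7), about twice the 5% implied; it is 9.7% by arcsine, 13.8% with Fisher's test and about 15% with the most conservative methods tried.

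This rests on 20.2% versus 6.4%, a two-sided 5% test, pooling over e-cigarette arm and all 240 participants counted. The cited rates equal 19/94 and 6/94, and section 2.2 reports 94 randomised per arm in the earlier trial. They therefore look like intention-to-treat rates (an inference), in which case 240 is the matching denominator and no further deduction for dropout is needed. A completer analysis would lower the power further.

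The figure should be corrected, but it is no reason to change the sample size, which NNAL determines.

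**What to change.** In section 8.2, replace the claim of over 95% power with a statement such as: about 89% power (two-sided 5% normal-approximation test of two proportions, 20.2% versus 6.4%, 120 VLNC versus 120 NNC participants pooled over e-cigarette arm, all randomised participants analysed). If the figure came from other inputs, state them and reconcile them with the 240 randomised in section 8.1 and the two-sided rule in section 8.3.

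The cost is one sentence. Sample size, tests and conduct are unchanged.

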8.3 Statistical methods

Basic baseline statistics including means (standard deviations) and frequency distributions (percentages) will be reported for demographic characteristics, smoking characteristics, nicotine dependence, and nicotine and toxicant exposure. Characteristics will be reported by the four treatment arms to identify treatment arm imbalances. Numerical baseline characteristics will be compared among four arms using ANOVA tests or nonparametric Kruskal-Wallis tests when appropriate. Categorical variables will be compared using chi-square tests or Fisher's exact tests. The focus of the statistical analysis will be the difference between four trial arms in terms of the biomarkers of toxicity and health effects. Analyses will be conducted in two approaches, which will address our research questions in two different angles. The first approach is a simplified and streamlined one, the longitudinal measurements of these biomarkers over the 16-week period will be summarized by using just the baseline (visit 3, pre-randomization) and final (visit 7, end of randomization period) measurements. Analysis of Covariance (ANCOVA) models will be used to compare the final measurements among the four arms, while the baseline measurements will be treated as controlled covariates in the model. Specifically, the comparisons between arms 1 and 3 and between arms 2 and 4 answer whether switching to very low nicotine cigarettes leads to lower markers of harm as compared to continuing on normal nicotine cigarettes. This addresses specific Aim 1. Furthermore, we will study if this reduction is the same when combined with 5% nicotine e-cigs (arms 1 and 3) and combined with placebo e-cigs (arms 2 and 4). Similarly, comparison between arm 1 and arm 2 reveals if access to nicotine versus placebo e-cigs impacts these biomarkers. This will address Aim 2. In particular, we will test if the arm 3 has the best outcome as stipulated in Aim 2. These analyses will be conducted using ANCOVA models with interaction terms between traditional cigarettes (normal nicotine vs. very low nicotine) and e-cig (5% vs. 0%). Appropriate transformation may be done on some of the outcome variables (for example log-transformation) to make sure the underlying statistical assumptions are all satisfied. Note that for NNAL, one of our main biomarkers of toxicity; it can only be analyzed using the first approach due to the limitation of number of measures.

The second approach for biomarker analysis will use the longitudinal data analysis to model all the repeated measurements of these biomarkers over the entire 16 weeks. Their trajectories will be plotted for each of the 4 arms. Linear mixed-effect models will be used to model the biomarker measurements on the following predictors: time after randomization (X1, which can be measured in weeks (continuous or visit number (categorical))), normal vs. low nicotine cigarettes (X2), 5% nicotine e-cig vs. placebo e-cig (X3), the interaction between cigarette and e-cig (X2*X3), and the interaction between X1 and X2, X3, X2*X3. In particular, the three-way interaction of X1, X2 and X3 indicates an interaction between cigarette type (NNC versus VLNC) and e-cig type (nicotine versus placebo) on their effect on the change of these markers of harms to health over time. Note that the time variable (X1) can be treated as either categorical or continuous, which will lead to different statistical models – growth curve model vs repeated-measure ANOVA models. If X1 is treated as categorical, then the estimated means and 95% confidence interval (CI) values of the outcome variables will be reported using tables. If X1 is treated as continuous, then the point estimates and 95% CI of the coefficients (rate of changes) will be reported. The baseline (before randomization) measures of the outcome variables will be included in the model as a controlled covariate. Family-wise type-I error rate due to multiple comparisons will be controlled at the visit level (if X1 is treated as categorical) using Bonferroni method. Again, appropriate transformation of the outcome variable may be carried out – similar to the first approach.

Intent-to-treat (ITT) principle will be adopted for the analyses in both approaches. Additionally, the measurements of tobacco use and addiction and measurements of mental health will be monitored and summarized, and will be compared across these arms in a similar statistical fashion as described above. Self-reported compliance will be reported for all participants. For participants in arm 4 (VLNC plus placebo ecigs) their compliances will be further evaluated using biomarkers. Comparison on the outcome variables will be made between compliers vs non-compliers within arm 4 participants only. All analyses will be conducted using statistical software SAS version 9.4 or higher (SAS Institute, Cary, NC, USA) and R Programming language version 3.6.1 or higher (R Foundations). All tests will be two-sided and the statistical significance level to be used is 0.05.

Adjusted models will evaluate the treatment effect while adjusting for covariates, such as gender, age, race, SDOH scoring, and other baseline factors.

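### Section 8.3 does not restate the 0.05/3 level or the three arm 3 contrasts on which 8.2 sized the NNAL comparison, and its test that arm 3 is best has no decision rule

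*Combined protocol and SAP*

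**What the plan says.** Section 1.2 makes urinary NNAL at Week 16 the primary endpoint. Section 8.2 sizes the trial on it: "Let arm 3 of the trial be the group to which arms 1, 2 and 4 will each be compared". It continues: "To adjust for multiple comparisons, the type one error level alpha is taken to be" 0.05/3 = 0.017. With an effect of 0.58 SD, it gives 60 per arm for 80% power.

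Section 8.3 assigns contrasts to aims. For Aim 1: "Specifically, the comparisons between arms 1 and 3 and between arms 2 and 4 answer whether switching to very low nicotine cigarettes" lowers the markers of harm. For Aim 2: "Similarly, comparison between arm 1 and arm 2 reveals if access to nicotine versus placebo e-cigs impacts these biomarkers. This will address Aim 2". It adds: "In particular, we will test if the arm 3 has the best outcome as stipulated in Aim 2". On the model it says: "These analyses will be conducted using ANCOVA models with interaction terms between traditional cigarettes" and e-cigarette type. The same section makes every test two-sided at 0.05. Its only multiplicity rule, Bonferroni by visit, sits in the mixed-model approach with categorical time. Of NNAL it says that "it can only be analyzed using the first approach due to the limitation of number of measures", and that first approach is the ANCOVA.

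In section 1.1, Aim 2 compares nicotine with zero-nicotine e-cigarettes and singles out no arm. The combination used in arm 3 appears in the central hypothesis.

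**The concern.** Two adjacent sections describe the confirmatory analysis of the same endpoint differently. Only 1v3 is named in both. The level that justified 60 per arm does not reappear where the tests are specified, and the multiplicity rule that does appear cannot reach NNAL.

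The same result could therefore be read in opposite ways: 1v3 with p = 0.03 is positive at 0.05 and negative at 0.017. A reader also cannot tell which results would establish that arm 3 is best. The one e-cigarette contrast named for Aim 2 is among normal-nicotine cigarette users. The matching contrast among very-low-nicotine users, 3v4, is one that 8.2 sized and 8.3 does not name.

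**Working it through.** **Inputs.** From 8.2: 60 per arm, effect 0.58 SD, alpha 0.05/3. From 8.3: two-sided tests at 0.05. My assumptions: independent arm means, normal approximation and, unless stated, no missing Week 16 NNAL.

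**The contrasts side by side.**

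| Contrast | Sized in 8.2 at 0.05/3 | Named in 8.3 |
|---|---|---|
| 1v3 | yes | Aim 1 |
| 3v2 | yes | no |
| 3v4 | yes | no |
| 2v4 | no | Aim 1 |
| 1v2 | no | Aim 2 |

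**Reproducing 8.2.** The standardised difference is 0.58 × √(60/2) = 3.177. The two-sided critical value at 0.05/3 is 2.394. Power = Φ(3.177 − 2.394) = Φ(0.783) = 78.3%, within 2 points of the stated 80%. At 0.05, power is Φ(3.177 − 1.960) = 88.8%, and 47 per arm would give 80%. The planned 60 per arm therefore depends on the 0.05/3 correction.

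**Family-wise error when all arms are equal.**
- Aim 1 pair at 0.05: 1v3 and 2v4 share no arm, so 1 − 0.95² = 9.75%.
- Aim 2, 1v2 alone at 0.05: 5%.
- All three as one family: 13.0% by simulation (Bonferroni bound 3 × 0.05 = 15%; 1 − 0.95³ = 14.3% if independent).
- The 8.2 family at 0.05/3 each: about 4.5% by simulation.

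**If only arm 3 differs, by 0.58 SD.**
- 1v2: the true difference is zero, so it rejects at its nominal 5%.
- 3v4: 78.3% power at 0.05/3, 88.8% at 0.05.
- Interaction: 0.58 × √60 / 2 = 2.246, so Φ(2.246 − 1.960) = 61% at 0.05.

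**Power for arm 3 to be significantly lower than all three arms,** by simulation with 0.58 SD against each:

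| Rule | 60 per arm | 48 per arm (20% loss assumed) |
|---|---|---|
| 0.05/3 each | about 59% | about 43% |
| Holm at overall 0.05 | about 75% | about 61% |

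The 20% is illustrative. Section 8.2 makes no allowance for loss after randomisation, and the 300 enrolled to randomise 240 in 8.1 covers only losses before it.

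**The case against.** The strongest reply is that 8.3 has not abandoned 8.2. The pair 1v3 is in both. A test that arm 3 is best, read with 8.2, naturally means 3v1, 3v2 and 3v4. A 0.05 significance level can be an overall level, since 8.2 itself divides 0.05 by three. This stands in part: a reader might infer that the 8.2 family was dropped, and the documents do not support that. They leave open whether it was carried over, because 8.3 gives no contrasts, no alpha and no statement whether arm 3 must beat all the other arms or any one of them.

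Second, the 13.0% should not be read as the plan's error rate. It pools two separately stated aims on different factors, which is a judgement. By aim the figures are 9.75% and 5%.

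Third, a reader might infer that the plan cannot estimate the e-cigarette effect among very-low-nicotine users. It can: the ANCOVA with interaction supplies both 3v4 and the pooled effect. What is missing is their naming and status. The 61% for the interaction and the 78% for 3v4 also concern different estimands, so they do not rank two tests of one hypothesis. The scenario in which only arm 3 differs is itself an assumption.

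Fourth, Aims 1 and 2 are worded as overall factor effects, so making the 8.2 contrasts confirmatory and 2v4 and 1v2 secondary is partly a design choice. That also stands, and the choice belongs to the sponsor.

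**Conclusion.** The inconsistency is in the text and should be fixed. Taken literally, 8.3 tests the primary endpoint at a looser level than the one that set the sample size, on a set of pairs that shares only 1v3 with 8.2. Under the global null this means 9.75% for Aim 1 and 5% for Aim 2 (13.0% only if they form one family), against about 4.5% under 8.2. If only arm 3 differs, the sole named Aim 2 contrast has no power beyond its nominal 5%, while 3v4 has about 78% at 0.05/3. The reference to Aim 2 in the arm 3 sentence should point to the central hypothesis.

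The power figures rest on 0.58 SD, equal arms of 60 and complete Week 16 NNAL. I take 0.58 as given: the cited-trial figures in 8.2 alone give 0.248/0.562 = 0.44, but 8.2 says that it combines two data sets. Nothing here shows that 60 per arm is wrong for the 8.2 family.

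**What to change.** State in 8.3 one confirmatory NNAL family and its alpha, and reconcile it with 8.2.

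- The family the trial was sized for is 3v1, 3v2 and 3v4 from the baseline-adjusted ANCOVA, at 0.05/3 each or with Holm at an overall 0.05.
- If the sponsor keeps the aim-based contrasts as confirmatory, apply the same family-wise control to them and restate the power in 8.2 for that family.
- Say that the general 0.05 in 8.3 is the overall level and does not override this for NNAL.
- Define arm 3 best as significantly lower than all three other arms, and refer it to the central hypothesis. If power for this claim is stated, give its assumptions and a range for missing data, as in the table above.
- For Aim 2, report 1v2, 3v4 and the pooled e-cigarette effect (arms 1 and 3 against arms 2 and 4) with 95% confidence intervals. Label every contrast outside the confirmatory family as secondary.

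The data and model do not change. The cost is about 78% power per contrast at 0.05/3 instead of 89% at 0.05, but 0.05/3 is the level 8.2 already planned for. With the 8.2 family, each aim is confirmed in one stratum only: Aim 1 among nicotine e-cigarette users (1v3), Aim 2 among very-low-nicotine cigarette users (3v4). The contrast 3v2 changes both factors.

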1.0 Objectives

1.1 Study Objectives

The long term goal of this project is to determine the likely health effects of very low nicotine content in cigarettes, in conjunction with availability of nicotine-containing electronic cigarettes (e-cigs) among smokers with mental health conditions (SMHC). This will be tested in a rigorous randomized controlled trial design. We plan to use a comprehensive set of measures of proven validity and reproducibility, including toxicant exposure, addiction and mental health to assess these effects. The specific objective of this study is to recruit a cohort of 240 current exclusive daily SMHC (diagnosed using the MINI International Neuropsychiatric Interview) and to measure a comprehensive battery of behavioral and health indicators at 4 and 8, 12 and 16 weeks after being randomized to use either normal nicotine content (NNC) Spectrum cigarettes (11.6 mg nicotine/cigarette) or very low nicotine content (VLNC) Spectrum cigarettes (0.2 mg nicotine/cigarette) while also having access to a JUUL e-cig (JUUL Labs, Inc.) containing either 0% or 5% nicotine strength e-liquids in a randomized double-blind, placebo-controlled 2 by 2 design. Our central hypothesis is that key markers of harms to health (e.g. urinary NNAL, exhaled CO, measures of addiction, and mental distress) will be significantly improved among SMHC who are provided very low nicotine cigarettes and high nicotine e-cigs. Study aims are:

Aim 1: To determine whether SMHC have lower levels of markers of harm (e.g. urine NNAL, exhaled CO, measures of mental health) and cigarette addiction when switched to VLNC cigarettes, as compared with NNC cigarettes, at the end of the randomized phase (week 16).

Aim 2: To determine whether SMHC have lower levels of markers of harm (urine NNAL, exhaled CO) and cigarette addiction when provided with nicotine-containing versus zero nicotine electronic cigarettes, at the end of the randomized phase (week 16).

Aim 3: To determine whether use of VLNC cigarettes increases the proportion of smokers who completely switch away from combustible tobacco use (no cigarette use in the past 7 days and CO < 6ppm), as assessed (a) at the end of the randomized phase (week 16) and (b) 4 weeks after the end of the randomized phase of the trial (week 20), compared to those using NNC cigarettes.

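### Section 8.3 names only arm 1 versus arm 2 as the e-cig contrast for Aim 2; for NNAL, neither the contrast in very-low-nicotine smokers nor an all-arm e-cig effect is tied to that aim

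*Combined protocol and SAP*

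**What the plan says.** Section 1.1 states Aim 2 for smokers with mental health conditions in general: markers of harm and cigarette addiction "when provided with nicotine-containing versus zero nicotine electronic cigarettes, at the end of the randomized phase (week 16"). It sets no condition on cigarette type. Section 7.4.2 defines the arms: 1 and 2 smoke normal-nicotine cigarettes with 5% and 0% e-cigs respectively; 3 and 4 smoke very-low-nicotine cigarettes with 5% and 0% e-cigs.

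Section 8.3 then links contrasts to aims. For Aim 1 it uses both e-cig strata: "the comparisons between arms 1 and 3 and between arms 2 and 4 answer whether switching to very low nicotine cigarettes" lowers markers of harm. For Aim 2 it names one pair: "Similarly, comparison between arm 1 and arm 2 reveals if access to nicotine versus placebo e-cigs impacts these biomarkers. This will address Aim 2". Two further sentences follow: "In particular, we will test if the arm 3 has the best outcome as stipulated in Aim 2", and "These analyses will be conducted using ANCOVA models with interaction terms between traditional cigarettes" and e-cig type. The same section confines NNAL, the primary endpoint in 1.2, to this first (ANCOVA) approach.

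Section 8.2 sizes the trial on a different set of comparisons: "Let arm 3 of the trial be the group to which arms 1, 2 and 4 will each be compared".

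**The concern.** The contrast that 8.3 says will address Aim 2 is the e-cig effect among smokers who keep normal-nicotine cigarettes. Sections 2.1 and 2.3 motivate the trial by a low-nicotine cigarette standard with e-cigs available, and the named contrast has nothing to say about smokers in that situation. Aim 1 gets both strata and Aim 2 gets one, without explanation. The e-cig comparison that 8.2 does power, arm 3 versus arm 4, is not the one assigned to Aim 2.

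At stake is what can be concluded about Aim 2 on the primary endpoint. Followed literally, a null arm 1 versus arm 2 result could be reported as the answer even if nicotine e-cigs had a clear effect under very-low-nicotine cigarettes. Followed loosely, the team could choose among arm 1 versus 2, arm 3 versus 4 and an average after seeing the data.

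**Working it through.** **Inputs.** 60 per arm, 240 in total (8.1); allocation 1:1:1:1 (7.4.3); planning effect 0.58 SD, alpha 0.05/3 rounded to 0.017, target power 80% (8.2); two-sided tests at 0.05 (8.3). Effects are in SD units. Complete data and no precision gain from the baseline covariate are assumed.

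**The plan's own figure.** For one comparison with arm 3, the standard error is √(2/60) = 0.183 SD.
- 0.58/0.1826 = 3.177. Subtracting the critical value 2.387 (two-sided 0.017) leaves 0.790, so power is about 78.5% by normal approximation (77.4% with the t distribution).
- The size needed for 80% is 62 per arm by normal approximation. The stated 60 per arm and 80% are reproduced approximately, slightly on the optimistic side.

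**Contrasts set side by side.**

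| Contrast | Question | Tied to Aim 2 in 8.3? | Powered in 8.2? |
|---|---|---|---|
| 1 v 2 | e-cig effect, normal-nicotine cigarettes | Yes | No |
| 3 v 4 | e-cig effect, very-low-nicotine cigarettes | Not named | Yes |
| 1+3 v 2+4 | e-cig effect averaged over cigarette type | Not named | No |
| 3 v 1 | cigarette effect with 5% e-cigs | No (Aim 1) | Yes |
| 3 v 2 | both factors changed together | Not named | Yes |
| Arm 3 best | statistic not defined | Yes | Not as such |

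**Precision.** Arm 1 v 2 compares 60 + 60 = 120 of 240 participants, which is 50%. In a four-arm ANCOVA the other two arms help only to estimate the residual variance and the baseline slope.
- 1 v 2: SE = √(2/60) = 0.183 SD.
- 1+3 v 2+4: SE = √(2/120) = 0.129 SD.
- Ratio: 0.183/0.129 = 1.41.
- Effect detectable with 80% power at two-sided 5%: (1.960 + 0.842) × 0.1826 = 0.51 SD for 1 v 2, and 2.802 × 0.1291 = 0.36 SD for the average.

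**Power if the e-cig effect is the same in both strata** (noncentral t, two-sided 5%; the effect sizes are assumptions):

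| Effect (SD) | 1 v 2 | Averaged, 1+3 v 2+4 |
|---|---|---|
| 0.3 | 37% | 64% |
| 0.4 | 58% | 87% |
| 0.58 | 88% | 99% |

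Normal-approximation check at 0.4 SD: 0.4/0.1826 − 1.960 = 0.231, giving 59%; 0.4/0.1291 − 1.960 = 1.138, giving 87%.

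**Power if the effect differs by stratum** (normal approximation, two-sided 5%, assumed effects):
- 0.29 SD under normal-nicotine and 0.58 SD under very-low-nicotine cigarettes: 1 v 2, 36%; 3 v 4, 89%; average (0.435 SD), 92%.
- None under normal-nicotine and 0.58 SD under very-low-nicotine cigarettes: 3 v 4, 89%; average (0.29 SD), 61%. Arm 1 v 2 then has no effect to detect.

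The 0.58 SD in 8.2 comes from reduced-nicotine cigarette trials, so applying it to an e-cig effect is an assumption.

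**The case against.** The strongest reply is that the very-low-nicotine arms are not ignored. The sentence after the Aim 2 statement adds the arm 3 test, and showing that arm 3 is best must involve arm 4. The next puts these analyses in an ANCOVA with a cigarette-by-e-cig interaction. Section 8.2 powers arm 3 versus arm 4, and the longitudinal model in 8.3 includes an e-cig term across all four arms. This stands to the following extent: a reader might infer from the Aim 2 sentence that very-low-nicotine smokers are left out of the e-cig analysis altogether, and the documents do not support that.

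It does not settle the point. The arm 3 test has no stated statistic, and arm 3 could beat arms 1 and 2 because of its cigarettes alone. Aim 2 as written does not stipulate that arm 3 is best; that is closer to the central hypothesis in 1.1. An interaction ANCOVA is a model, and it can yield any of these contrasts. With 0/1 coding and normal-nicotine cigarettes as reference (coding is not stated), the e-cig coefficient would itself be arm 1 versus arm 2. The longitudinal model does not cover NNAL.

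A second reply is that averaging is not always better. This also stands: if the effect exists only under very-low-nicotine cigarettes, arm 3 versus arm 4 (89%) outperforms the average (61%). Simple effects with an interaction are a legitimate factorial analysis.

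**Conclusion.** The Aim 2 estimand for NNAL is underspecified, and the one e-cig contrast tied to it is narrower than the aim. The named contrast compares half the randomized participants and is not one of the comparisons powered in 8.2. If the e-cig effect is similar across cigarette types, its standard error is 1.41 times that of the averaged effect (58% against 87% power at an assumed 0.4 SD). If the effects differ, it cannot show what happens under very-low-nicotine cigarettes. These figures assume complete data and no baseline gain.

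Two stronger readings should be avoided. One is that 8.2 implies only 5% power for arm 1 versus arm 2. That requires arms 1, 2 and 4 to share a mean, which 8.2 does not state, and 5% is then simply the type I error rate under a true zero difference. The other is that the averaged effect should be the sole answer, or that Aim 1 should be recast in the same way. Both are trade-offs, and 8.3 already names both strata for Aim 1, so Aim 1 needs no change.

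**What to change.** Replace the Aim 2 sentence in 8.3 with: *Aim 2 is addressed by the nicotine versus placebo e-cig effect in both cigarette strata (arm 1 v 2 and arm 3 v 4) from the four-arm ANCOVA, reported with the effect averaged over cigarette type (arms 1+3 v 2+4) and the interaction, each with a 95% CI.*

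Align this with 8.2. Say how these contrasts relate to the three comparisons with arm 3, and whether arm 3 versus arm 4 is tested at 0.017 (8.2) or 0.05 (8.3). Define the arm 3 best-outcome test, or attribute it to the central hypothesis in place of Aim 2.

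The cost is wording only: the model and data are already planned, and no participants are added. It should be settled before unblinding. The downside is that the average must be read beside the two simple effects if they differ. The interaction that would show a difference is imprecise: its SE is √(4/60) = 0.258 SD, so its 95% CI extends about 1.96 × 0.258 = 0.51 SD either side.
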